In this 5-year NIH-funded research project (current NIH grant # R01MH123352), we propose an intervention entitled “WeTest-WeLink” that aims to (i) promote uptake of HIV self-testing among MSM in China, and (ii) linkage to care for MSM who obtain preliminary positive HIV self-test results. This proposal builds on years of formative work with MSM in China conducted by this team of investigators (previous NIH grant # R34MH106349), demonstrating promising effects from a pilot RCT and strong indication of intervention acceptability, feasibility, and cultural sensitivity. The intervention uses the “WeChat” mobile app platform, which offers multiple features built into the app that facilitate health information delivery and communication channels (e.g., capacity for private texts, group chats, video sharing, GPS, instant messaging, real-time audio and visual communication). This protocol is funded by the US National Institutes of Health, and includes three phases of research activity over 5 years. **Phase 1** (Year 1) involves use of online focus groups to refine the WeTest-WeLink intervention to incorporate additional and updated content regarding: the HIV care continuum, linkage to care for HIV-positive people and ART treatment; support and affirmation for those testing HIV-positive; and programming of GPS resources to assist participants in identifying care. Identification and incorporation of additional updated content will be guided by the Information-Motivation-Behavioral (IMB) theory of behavior change and Minority Stress Theory, and based on findings from focus groups to be conducted with MSM from study settings. **Phase 2** (Years 2-4) is a prospective 2-group RCT of 1,800 MSM recruited from 3 sites: Chengdu, Suzhou, Wuhan. Participants will be randomized to the control group or to the WeTest-WeLink intervention. Primary and secondary outcomes include: i) repeat HST at 6, 12, and 18-month follow-up, ii) linkage to care for those who test HIV-positive. Additional analysis will explore effects on behavioral HIV risk, engagement in HIV community-based prevention services, and theoretical mechanisms of behavior change. **Phase 3** (Year 5) involves qualitative examination with key constituents regarding implementation features specified within the CFIR.

RESEARCH PROTOCOL

Title: Mobile Health Intervention to Increase HIV Self Testing and Linkage to Services for High-Risk Men in China

Specific Aims

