The overarching objectives for this R01 research project are to test the effectiveness of an mHealth intervention entitled “WeTest-WeLink” that will increase repeat HIV self-testing (HST) among MSM, and to examine the efficacy of “WeTest-WeLink” on linking individuals who test positive to HIV care. Based on a successful 3-year R34 NIMH-funded pilot study conducted in Hefei, Anhui Province, we established proof-of-concept for the use of the WeChat app to promote HIV self-testing with MSM. In the current 5-year R01 NIMH-funded research, we will employ a user-centered design process to refine and expand app features (e.g., app-based HIV and health promotion messages, videos, GPS maps, private groups and two-way communication channels) to support repeat HST uptake, behavioral risk reduction, stigma coping strategies, and self-efficacy to link to HIV care. With the goal of increasing sustainable behavioral changes and examining the scalability of this proposed intervention, we will subsequently conduct a formative evaluation on the implementation of the intervention. The goal of this R01 application will be accomplished by using an Effectiveness-Implementation Hybrid Type 1 design consisting of a three site, 2-arm RCT to quantitatively test the intervention’s effects on primary and secondary outcomes (repeat HST, linkage to HIV-related care) as well as qualitative research to examine implementation and scalability. We will recruit 1,800 HIV negative MSM, who will be allocated to the intervention (access to the WeTest-WeLink app) or control group (basic information about HST and passive referral to HIV care for individuals who test HIV positive). We will assess participants at 6-, 12-, and 18 months to measure intervention effects on primary outcomes: use of HST (including photographic confirmation) and linkage to care for individuals who test HIV-positive. Secondary outcomes include sexual risk behaviors and use of HIV prevention services, and we will conduct mediation analysis to examine theoretical mechanisms of behavior change. We will qualitatively assess intervention-related process characteristics that enable and/or impede implementation and scalability informed by the Consolidated Framework for Implementation Research (CFIR).

The aims of this 5-year research program are the following:

Specific Aim 1. To evaluate the effectiveness of the WeTest-WeLink intervention on HST behaviors

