Hypothesis 1: Greater proportion of HST every six months, confirmed by photographic evidence of test results, in the intervention vs control group

Specific Aim 2. To evaluate the efficacy of the intervention on linkage to HIV related care

Hypothesis 2. Greater proportion of participants who test HIV+ in the intervention will be linked to care vs control group

Specific Aim 3. To inform broad scale implementation by assessing intervention barriers, facilitators, and potential adaptations for optimal uptake and sustainability

Hypothesis 3. Key informants will identify key intervention features that can enhance subsequent implementation and scalability in real-world, ecological settings

Background

Studies of MSM in China have found that stigma contributes to the underutilization of HIV prevention and testing services and to the underestimation of personal HIV risk behaviors. Many MSM refrain from accessing HIV prevention and testing offered through health clinics or local Centers for Disease Control (CDC) offices, out of fear of disclosing their same-sex behavior to physicians or CDC officials. A systematic review found that 62% of Chinese MSM had not been tested in the past 12 months and about half of them had never been tested for HIV in their lifetime. Low rates of testing and undiagnosed HIV infection pose substantial risks for furthering the growth of China's HIV epidemic. Interventions are urgently needed to increase rates of HIV testing for MSM in China as well as to facilitate linkage to care for those who test positive in order to disrupt the expanding epidemic in this population.

The use of mobile technologies to promote healthier behaviors ("mHealth") opens new avenues for support the use of HST. Emerging data suggest that delivery of HIV-prevention messages via mobile phone "apps" represents a feasible and acceptable way to encourage HIV testing and to lower HIV risk behaviors. In the context of HST, mobile phone apps can send text or video instruction on specimen collection and test result interpretation. In addition, automated app-delivered messages can provide timely, confidential, and convenient information to motivate risk reduction, retesting, and necessary referrals to care.

Preliminary Research

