Over a 3-month outreach and recruitment period, the study team recruited and enrolled 100 MSM participants into the pilot RCT and examined the acceptability, feasibility, and 6-month outcomes on HIV testing and condom use. All participants enrolled (100%) were retained at 6-month follow-up. At follow-up, participants in the intervention group had increased uptake of oral HST following baseline procedures (adj. RR=2.17, 95%CI: 1.08-4.37) and increased trust in use of oral HST (adj. RR=2.28, 95%CI: 1.15-4.51), compared to the control. Nearly all (98%) of those who reported using HIV self-test kits uploaded and submitted photographic confirmation of their test

results to study staff via the secure WeChat project portal. This high submission rate is indicative of the potential utility for remote health workers to counsel, refer, and provide linkages to care for people who test positive. Overall, 10 individuals tested positive and all received immediate linkages to care. In qualitative exit interviews, intervention participants commented favorably about app-based approach for supporting HST and prevention, the ability to communicate with online remote counselors for questions and referrals, the discrete nature of the app as a way to avoid uncomfortable disclosure, and the focus on MSM-based support and identity affirmation. These results provide compelling support for the feasibility and acceptability of WeTest, and demonstrate the team's ability to recruit and implement a mHealth intervention for this population.

Methods

This 5-year project involves 3 phases of research.

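### Hypothesis 2 compares linkage only among men who test HIV-positive, a group formed after randomisation, so a difference in it cannot by itself be read as the app's effect on linkage

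*Combined protocol and SAP*

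**What the plan says.** Specific Aim 2 is to evaluate the intervention's efficacy on linkage to care. Its hypothesis is "Greater proportion of participants who test HIV+ in the intervention will be linked to care vs control group". The outcome statement in the Specific Aims has the same restriction, "linkage to care for individuals who test HIV-positive", and so do the opening summary and the Phase 2 paragraph under Methods, "linkage to care for those who test HIV-positive". None of these three states a proportion.

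On entry status, the Specific Aims say "We will recruit 1,800 HIV negative MSM". On what the app should change, Hypothesis 1 expects "Greater proportion of HST every six months, confirmed by photographic evidence of test results, in the intervention vs control group", and the Specific Aims describe app features intended "to support repeat HST uptake, behavioral risk reduction, stigma coping strategies, and self-efficacy to link to HIV care".

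The Preliminary Research section gives a 6-month pilot adjusted RR of 2.17 (95% CI 1.08 to 4.37) for uptake of oral self-testing. It also reports 10 positive men, all linked, without splitting them by arm.

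One sentence of the Specific Aims lists linkage as a primary outcome. Another speaks of "primary and secondary outcomes (repeat HST, linkage to HIV-related care" without ranking them. The rank should be made clear, but that is a separate matter.

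**The concern.** Randomisation balances the 1,800 men at entry. It does not balance a subgroup whose membership depends on what happens afterwards. To enter the Hypothesis 2 denominator a man must become infected and then test, and the app is aimed at both steps.

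If Hypothesis 1 is right, the positives in the intervention arm will generally include men who would not have tested under control. If the app reduces risk behaviour, some men who would have been infected under control will be missing. Either change can make the two groups of positives differ in how readily they would link, whatever the app does for linkage itself.

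Aim 2 makes a causal claim and rests on this comparison. A lower proportion in the intervention arm could hide a real benefit, and a higher one could suggest a benefit that does not exist.

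**Working it through.** The documents give no expected number of positives, linkage rate, power or significance level for Hypothesis 2, so there is no planned figure to reproduce. What follows is illustrative. From the documents: the pilot RR and its limits, the 10 of 10 linked, and 1,800 men. Assumed: everything else, including equal arms of 900.

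**Testing pathway.** Assume equal infection in both arms, no true effect on linkage, and that every man who would test under control also tests under intervention. Let R be the ratio of testing among infected men, intervention to control. The share of intervention-arm positives who tested only because of the app (induced testers) is 1 − 1/R. The spurious difference is (1 − 1/R) × (linkage in induced testers − linkage in the others).

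With 80% linkage in the others and 70% or 90% in induced testers:

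| R | Induced share | Observed linkage, intervention (control 80%) | Spurious difference, points |
|---|---|---|---|
| 1.08 (pilot lower limit) | 7.4% | 79.3% or 80.7% | −/+ 0.7 |
| 1.2 | 16.7% | 78.3% or 81.7% | −/+ 1.7 |
| 1.5 | 33.3% | 76.7% or 83.3% | −/+ 3.3 |
| 2.17 (pilot estimate) | 53.9% | 74.6% or 85.4% | −/+ 5.4 |
| 4.37 (pilot upper limit) | 77.1% | 72.3% or 87.7% | −/+ 7.7 |

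The pilot RR is for 6-month uptake in all participants, not cumulative testing in infected men. Suppose 2.17 held in each of three independent six-month windows with control testing c of 20% to 40% per window. The ratio over k windows is [1 − (1 − 2.17c)^k] / [1 − (1 − c)^k]. For men infected at the start (k = 3) it is 1.68 at c = 20% and 1.27 at c = 40%. With infections spread evenly (numerator and denominator each averaged over k = 1, 2, 3) it is 1.84 and 1.56. The difference is then 10 × (1 − 1/1.27) = 2.1 to 10 × (1 − 1/1.84) = 4.6 points. If the same men test in every window, the ratio stays nearer 2.17.

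**If linkage is near 100%.** With 98% in the others and 95% in induced testers, (1 − 1/R) × (−3) gives −0.5 points at 1.2, −1.0 at 1.5 and −1.6 at 2.17. The pilot's 10 of 10 has an exact 95% lower limit of 0.025^(1/10) = 69%, so it does not establish near-universal linkage.

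**Infection pathway.** The documents give no effect size. The pilot "examined the acceptability, feasibility, and 6-month outcomes on HIV testing and condom use", but no condom-use result is reported. Keeping a 10-point gap, take two equal groups of infected men linking at 85% and 75%, all of whom test. Control is (0.85 + 0.75)/2 = 80%.

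- Infection halved only in the 85% group: (0.425 + 0.75)/1.5 = 78.3%, or −1.7 points. Halved only in the 75% group: (0.85 + 0.375)/1.5 = 81.7%, or +1.7.
- A 20% cut in one group only: (0.68 + 0.75)/1.8 = 79.4% or (0.85 + 0.60)/1.8 = 80.6%, so −/+ 0.6.
- An equal cut in both groups: no difference.

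**Sampling error.** With 80% linkage, control testing of 40% and R = 1.5, the 95% half-width is 1.96 × √(0.16/n_control + 0.16/n_intervention).

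| Infected over follow-up | Positives, control vs intervention | Half-width, points |
|---|---|---|
| 3% | 10.8 vs 16.2 | 31 |
| 5% | 18 vs 27 | 24 |
| 10% | 36 vs 54 | 17 |

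**How the two denominators can disagree.** Take 5% infected, control testing of 40%, R = 1.5, no linkage effect and induced testers at 70%. The Hypothesis 2 proportion falls from 80% to 76.7%. Linked men per randomised man rise from 0.05 × 0.40 × 0.80 = 1.6% to 0.05 × 0.40 × (0.80 + 0.5 × 0.70) = 2.3%.

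**The case against.** The strongest reply concerns scope. The text supplied is in practice a Phase 1 focus-group protocol; Phase 2 appears in summary sentences, and Hypothesis 2 is one line among the aims, not a specified estimand or model. A reader might infer that the trial has no remedy. The documents do not support that: a fuller Phase 2 plan may exist and may deal with this. What stands is that the hypothesis and outcome, as worded, leave the problem open.

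The second reply is materiality. Every linkage rate above is assumed. The only observed figure is 10 of 10, and near that level the distortion is small. Sampling error exceeds every bias shown. This limits the size of the claim but does not remove it: a confidence interval makes no allowance for this bias, and more data do not shrink it.

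The third reply is that linkage among men who test positive is the question Aim 2 asks, and that an all-randomised outcome answers a different one. That is correct, and it is why the conditional proportion should stay.

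A reader might also infer that the comparison favours the app, because the app brings in more testers. Nothing in the documents says whether men prompted to test link more or less readily than others. The Background describes fear of disclosure as a barrier to services, which makes a difference plausible but does not fix its direction.

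**Conclusion.** The point holds for the hypothesis as worded. A between-arm difference in linkage among men who test positive cannot by itself be read as the app's effect on linkage, and the sign of the bias is unknown. The testing-route bias vanishes only if the app leaves testing among infected men unchanged, which runs against Hypothesis 1, or if induced testers link exactly as the others do.

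On a 10-point linkage gap, the size runs from under 1 point at the pilot's lower limit for testing to about 8 at its upper limit. The infection route adds a further possible 0.6 to 1.7 points in either direction, with no effect size in the documents behind it. These are illustrations, not estimates, and do not show that the bias will be large in this trial. The change is worth making because it is cheap and alters what Aim 2 can conclude.

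**What to change.** 1. Keep the Hypothesis 2 proportion, and label it a non-randomised comparison among men who test positive.
2. Beside it and the testing result, prespecify the proportion of all randomised men who tested HIV-positive during follow-up and were linked to care, by assigned arm. Use the same linkage window after the positive test in both arms. A fixed cut-off at 18 months would give a man who tests positive at that visit no time to link. State one rule for how men lost to follow-up count.
3. State that no causal claim about linkage will rest on the conditional proportion alone.
4. Optionally, add principal-stratum bounds for men who would test positive in either arm. These assume that the app stops no one from testing positive, which sits uneasily with its risk-reduction target, and they help mainly when testing differs little between arms. With a true gain from 80% to 90% and induced testers at 70%, they run from +4 to +20 points at R = 1.2 but from −5 to +20 at 1.5.

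The cost is wording plus one analysis of outcomes already planned. The all-randomised outcome has real limits:

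- It mixes testing, infection and linkage, and can be positive with no linkage effect.
- It counts prevented infections against the app. If all positive men link at the same rate, a cut in infections of 1 − 1/R cancels the testing gain: 17% at R = 1.2 and 33% at R = 1.5.
- Power is low. With 900 per arm, two-sided 5%, control testing of 40%, no linkage effect (80%) and induced testers at 70%:

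| Infected | R = 1.5: control vs intervention (power) | R = 1.2: control vs intervention (power) |
|---|---|---|
| 3% | 0.96% vs 1.38% (13%) | 0.96% vs 1.13% (6%) |
| 5% | 1.6% vs 2.3% (19%) | 1.6% vs 1.88% (7%) |
| 10% | 3.2% vs 4.6% (34%) | 3.2% vs 3.76% (10%) |

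It should therefore be reported alongside the conditional proportion and not in its place.

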Welcome and thank you for volunteering to take part in this focus group. You have been asked to provide feedback on a new WeChat public account /公众号 “WeTest-WeLink” we are developing to promote HIV self-testing and to assist linkage to HIV care or prevention services. We want to sincerely express our appreciation for your time and input.

Introduction: This focus group discussion is designed to gather your thoughts and feelings regarding “WeTest-WeLink”. We will show you various components of “WeTest-WeLink” and ask your feedback regarding content, applicability, features, and visual attractiveness. The primary purpose of this discussion is to capture feedback from potential users like you, and thus all candid feedback is appreciated. This focus group discussion will take no more than 90 minutes. As we informed you earlier, we would like to record this audio component of this discussion to help us remember and review comments from this group discussion. If anyone has a concern with recording. We will not be recording the visual component of this discussion. If anyone has concerns about recording the audio discussion, please use the Zoom/WeChat function to notify the research assistant, and that person will discuss your concerns privately. (Switch on the recorder on Zoom/WeChat for all members who remain in the discussion).

Confidentiality: Despite being audio recorded, I assure you that the discussion will be confidential. The recording will be stored in a highly secured server until it is transcribed word for word, and then it will be destroyed. Recordings will be accessed only by the study team through secure means. The transcribed notes of the focus group will contain no information that would allow individual participants to be linked to specific statements. You should try to answer and comment as accurately and truthfully as possible. I and the other focus group participants would appreciate it if you would refrain from discussing the comments of other group members outside the focus group. If there are any questions or discussions that you do not wish to answer or participate in, you do not have to do so; however, we certainly welcome all feedback you may have during the course of the discussion.

Ground rules

- The most important rule is that only one person speaks at a time. There may be a temptation to jump in when someone is talking but please wait until they have finished.
- There are no right or wrong answers.
- You do not have to speak in any particular order.
- When you do have something to say, please do so. There are many of you in the group and it is important that I obtain the views of each of you, if you want to contribute.
- You do not have to agree with the views of other people in the group.

Does anyone have any questions? (answers) OK, let's begin.

Warm up

First, I'd like everyone to briefly introduce themselves. Can you tell us your given name (not your family name) or a nickname and tell us about one thing about yourself that you want to share with the group, such as your hobby.

WeTest WeLink Demonstration – First Round:

I am going to show you some sample content and layout of the content as it currently exists. I am going to show each feature, along with content examples in their entirety. Then, we will individually go through each feature and content example.

During this first round, I would like you to pay attention to the content, features, and layout.

(go over the “WeTest-WeLink” account)

First Round Discussion Questions: Overall Impression

- What are your general impressions of the content after seeing it for the first time?
- What do you think of the current layout?
- Are there features that quickly caused a positive reaction when you saw them?
- Are there features that gave you pause when you saw them?
- After seeing it for the first time, how many of you would be excited to start using it?
- Do you anticipate challenges or difficulties in using this account? If yes, what challenges do you anticipate? [continue with follow-up questioning to individuals/group members].
- What would make the account more ideal for promoting HIV self-testing and assisting people who need to access HIV care or prevention services?

Second Round Discussion Questions

OK, let's go through the demonstration a second time, but we will pause after each feature is shown.

1. HIV self-testing demonstration video

Guiding Questions:

- What do you think of the video?
 - Usability
 - Positive/negative aspects of content
 - Understandability of the content

2. HIV linkage to care demonstration video

Guiding Questions:

- What do you think of the video?
 - Usability
 - Positive/negative aspects of content
 - Understandability of the content
- 3. Other content: The account will house content in different forms of media (e.g. video, short readings, memes, or short mentoring vignettes)

Showing content is designed to provide information relevant to:

